1.2.4. FluGen's H3N2 (A/Singapore/INFIMH-16-0019/2016) M2SR vaccine

FluGen is developing a novel live virus vaccine platform known as "M2SR" to address the need for more effective influenza vaccines that will provide more consistent and broad-spectrum immunity for adults, and especially the elderly. The product is a live virus vaccine for intranasal administration that has been shown to provide protection against multiple influenza A subtypes in animal models (see below). The vaccine is a replication-defective recombinant influenza virus that does not express the essential M2 protein (and hence, the derivation of the "M2SR" naming convention [Single Replication phenotype due to lack of M2]). The M2SR vaccine virus backbone is comprised of (1) five of the six internal proteins of the donor virus Influenza A/Puerto Rico/8/34 (PR8), a strain that has been used for decades in traditional inactivated influenza vaccine manufacturing; (2) the sixth internal protein, M2, which is acquired from the cell substrate used to grow the vaccine virus, M2 Vero cells, which stably express and supply M2 protein for vaccine virus growth; and (3) the two influenza virus surface protein antigens, HA and NA, which can be derived from any selected Type A influenza strain. The resulting vaccine virus can infect normal cells in the respiratory epithelium of the vaccine recipient and then uncoat and initiate infection similar to a wild-type influenza virus, thereby evoking an immune response. However, because the M2SR genome does not encode for M2 protein, no viral progeny is subsequently produced after the initial (single round) infection, such that no cellto-cell spread or subsequent shedding of virus occurs.

Sing2016 M2SR is a recombinant, monovalent influenza A virus that contains an Influenza A/Puerto Rico/8/34 (PR8) backbone with nine amino acid changes distributed over five genes (PB1, PB2, PA, NP and NS1) that facilitate growth in the production cell line, M2VeroA. The mechanism of attenuation (deletion of the M2 gene) is not affected. The Sing2016 M2SR also provides the HA and NA components from A/Singapore/INFIMH-16-0019/2016 that were recommended for the 2018-2019 influenza season.

1.3. Clinical Experience

Previous clinical experience with the monovalent H3N2 M2SR vaccine platform includes a First Time in Human (FTIH) Phase 1 dose escalation study in healthy adults, a Phase 2a challenge study in healthy adults, a Phase 1b dose escalation study in healthy adults, and a recently completed Phase 1 safety and immunogenicity study in adolescents (9-17 years old). Details on design and conduct of these studies are provided in the Investigator's Brochure (IB). All studies are complete, and data are unblinded for the Phase 1a FTIH, Phase 2 challenge, and Phase 1b dose escalation studies. As of 31 January 2021, the Phase 1 adolescent study remains blinded as the database is being prepared for lock. A total of 410 adults and 43 adolescents have been enrolled in these studies to date.

In the Phase 1 FTIH study, 72 adults (24 subjects per dose level) received a single dose of Bris10 M2SR at levels of 10⁶, 10⁷ or 10⁸ TCID₅₀ and 24 subjects received saline placebo. In the challenge study, 52 adults received a single 10⁸ TCID₅₀ dose of Bris10 M2SR and 56 subjects received saline, with 48 M2SR and 51 placebo subjects subsequently challenged with a drifted

H3N2 strain. In the Phase 1b dose escalation study, 206 (of 250 targeted) adults received two doses of either placebo (\sim 20% of enrollment) or Bris10 M2SR at 10^8 TCID₅₀ (\sim 20%), Sing2016 M2SR in amounts of 10^8 , $10^{8.5}$, or 10^9 TCID₅₀ (\sim 60% of enrollment; 165 active treatment subjects total). In the Phase 1 study, 43 adolescents (out of 50 planned) received one intranasal administration of 10^8 TCID₅₀ dose of Bris10 M2SR vaccine or placebo, followed by one intramuscular administration of licensed QIV administered 3 months later.

In the Phase 1 FTIH and the Phase 2a challenge studies, a total of 76 adult subjects received the highest dose of Bris10 M2SR tested (10⁸ TCID₅₀) with no serious adverse events (SAEs) or adverse events (AEs) or other observations that would halt these studies. In addition, in the challenge study, 48 of 52 subjects who received the live, single-replication Bris10 M2SR virus (single dose of 10⁸ TCID₅₀) were subsequently challenged with a live, replicating influenza virus. A portion of those individuals experienced infection and symptoms after challenge, consistent with influenza (i.e., nasal edema, nasal dryness, nasal pain/irritation, nasal congestion, rhinorrhea), but at a frequency less than that observed among individuals in the same study who did not receive vaccine prior to challenge. Unblinded safety data from the FTIH, challenge and dose escalation studies show one and two doses of the vaccine to be well tolerated, with related AEs that were generally mild or moderate in severity. No additional safety concerns were identified after challenge in the Phase 2a study. Reviews of unblinded safety data from the studies in adult populations have not identified any safety concerns. Of the 43 adolescents enrolled in the blinded Phase 1 study, no safety concerns related to the M2SR vaccine have been reported.

1.4. Rationale for the Current Study

Currently available inactivated and recombinant influenza vaccines primarily aim to induce neutralizing antibodies that recognize mainly influenza HA and depend on a close match between the vaccine and circulating viruses, rendering them much less effective against drift viruses. In addition, while a strong relationship has been established between pre-existing T cell immunity and illness severity, inactivated vaccines do not elicit cellular immune responses and generally do not provide broadly cross-reactive (heterosubtypic) immunity needed to protect against divergent strains. Moreover, mucosal immune responses have also been associated with a reduction in influenza illness in experimental challenge models and with live influenza vaccines; however, mucosal antibody responses are not elicited by conventional inactivated vaccines. For example, the severity of the 2014-15 influenza season was due to mismatch between the circulating epidemic strain and the inactivated vaccine, resulting in VE of just 13%. In the 2018-2019 influenza season in the US, the inactivated vaccines displayed a VE estimate of only 9% (www.cdc.gov) against H3N2, again due to mismatch between the vaccine strain and the circulating seasonal H3N2 virus that had accumulated antigenic changes (i.e., "drifted"). These recent examples indicate the need for an influenza vaccine that can protect against seasonal influenza drift variants.

In contrast to currently licensed influenza vaccines, pre-clinical testing of M2SR vaccine has shown induction of broadly reactive immune responses against multiple influenza subtypes and heterosubtypic protection in animal models, including demonstration of robust systemic, cellular and mucosal immunogenicity, even in the presence of pre-existing anti-influenza immunity. In

a pre-clinical proof-of-concept study, Bris10 M2SR provided protection to ferrets against a drifted H3N2 challenge virus, A/Alaska/140/2015, a virus belonging to clade 3c.2a1.

Human clinical trial participants who received Bris10 M2SR (10⁸ TCID₅₀ dose) in the Phase 1a FTIH and Phase 2a studies also demonstrated broad-spectrum immune responses. In the FTIH study, vaccine induced serum and mucosal antibody responses were cross-reactive against multiple antigenically different H3N2 viruses including recent strains that belonged to the same clade (3c.3b) as the challenge virus used in the Phase 2a study.

Results from the Phase 2a challenge study showed that a single dose of 10⁸ TCID₅₀ M2SR vaccine was effective against challenge in subjects who responded to vaccination by mounting a serum humoral immune response. Subjects who demonstrated any increase from baseline in serum antibody response (~50% of the M2SR cohort) by microneutralization (MN) to the intranasal M2SR vaccine had lower viral load and influenza-like symptoms after challenge than placebo subjects. These results suggested that if higher dose levels of M2SR could further enhance the serum immune response to influenza, then efficacy could be provided for in a higher proportion of M2SR recipients. Thus, a subsequent Phase 1b study evaluated one and two administrations of investigational M2SR at dose levels up to 10-fold greater than the dose employed in the Phase 2a challenge study.

The follow-on Phase 1b study was conducted with 206 healthy adults ages 18-49 years to evaluate whether an increased dose or a two-dose regimen could increase the proportion of subjects who respond to the M2SR vaccine, as demonstrated with serum, mucosal, and cellular immune responses. An early review of the group unblinded data showed that the higher doses (up to 10^9 TCID₅₀) and two doses administered with a 28-day interval were safe and well-tolerated; no SAEs were reported and no halting rules were met. Preliminary immunology data demonstrated that a single administration of the higher dose indeed resulted in a significantly higher rate of response to the M2SR vaccine. Subjects who received the 10^9 TCID₅₀ dose of M2SR dose demonstrated 71% seroconversion rate (\geq 4-fold) for serum hemagglutinin (HA) antibody in contrast to 28% seroconversion among recipients of 10^8 TCID₅₀ (dose used in the phase 2a challenge study).

The purpose of this proposed, additional Phase 1b clinical study is to assess for the first time the safety, tolerability/reactogenicity, and immunogenicity of H3N2 monovalent M2SR vaccines in an older adult population. A group of 15 adults age 50-64 will be enrolled first to assess safety. The probability that an AE with prevalence of 20% or more would be detected in the 15 subjects is >95%. After a safety review, the study will enroll 105 adults ages 65 to 85 years of age. One dose of investigational vaccine will be given intranasally followed at least 28 days later by delivery of an age-appropriate licensed QIV that is a quadrivalent influenza vaccine (QIV) recommended for the 2021/2022 season. Licensed vaccines will be selected and supplied by the Sponsor so that all subjects, within an age cohort, receive the same vaccine product. The same Sing2016 M2SR vaccine that will be used in this study has previously been investigated in adults 18-49 years of age, as described above. Demonstration of broadly reactive responses in the older adult population, similar to those found to be protective against challenge in adults, would support further clinical development of the M2SR vaccine platform in this age group.

Consistent with CDC recommendations, all subjects participating in the study will receive the licensed influenza vaccine at least 28 days after administration of study investigational product

(IP). The timing of the administration of licensed vaccine also will depend upon the availability of licensed vaccine, which usually occurs by early September each season. It is anticipated that the window between IP and QIV administrations for subjects in Cohorts 1 and 2 will be more variable, but no less than 28 days. The first cohort is anticipated to receive the first dose of IP in June 2021, but QIV may not be available until September. The window for administration of licensed QIV to study participants in Cohort 3 will be 28 to 42 days after intranasal administration of M2SR. Subjects will be followed for AEs occurring within 28 days after intramuscular inoculation with the licensed product. Subject diaries will not be employed after licensed vaccine administration.

2. STUDY OBJECTIVES AND ENDPOINTS

2.1. Objectives

2.1.1. Primary Objective

The primary objective of the study is to assess the safety and tolerability of a single dose of monovalent Sing2016 H3N2 M2SR influenza vaccine delivered intranasally to healthy subjects 50 to 85 years of age.

2.1.2. Secondary Objectives

The secondary objectives are:

- To evaluate safety of QIV when administered at least 28 days after receipt of investigational M2SR vaccine.
- To assess the immunogenicity (serum and mucosal antibody responses) of one administration of 10⁹ TCID₅₀ Sing2016 M2SR vaccine.

2.1.3. Exploratory Objectives

The exploratory objectives are:

- To evaluate cell-mediated immune responses after IP administration.
- To evaluate additional vaccine-related immune responses (e.g., innate immunity) during the period of study participation.
- To assess the immunogenicity (serum and mucosal antibody responses) after administration of licensed, seasonal QIV vaccine when administered at least 28 days after one administration of 10⁹ TCID₅₀ Sing2016 M2SR vaccine.

2.2. Endpoints

2.2.1. Primary Endpoints

The primary endpoints are:

- The number and percentage of study participants who experience solicited local and systemic reactions during the 7 days after administration of investigational M2SR vaccine or placebo, as recorded through subject electronic diary (eDiary).
- The number and percentage of study participants who experience unsolicited AEs during the 28 days after administration of investigational M2SR vaccine or placebo and prior to administration of licensed QIV.
- The number and percentage of study participants who experience SAEs from the time of informed consent through 28 days after receipt of QIV.

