6.1.2. Screening Period

In a private, individual setting, subjects will be given a full explanation of the nature of the study and written informed consent (Institutional Review Board [IRB] approval will be obtained before any study-related assessment) will be carried out. Group consenting will not be permitted and subjects requiring a Legally Authorized Representative may not participate in this study.

Screening for eligible and consenting subjects will be performed within 28 days prior to randomization/IP administration. Subjects will be re-confirmed for eligibility on Day 1 (V01) prior to dose administration. Chemistry and hematology at V00 will serve as eligibility and baseline values unless collected more than 28 days prior to V01. In such case the lab tests will be redone to establish baseline only.

Subjects will have been consented and prescreened for influenza serosusceptibility under a separate, site-specific IRB-approved informed consent form (ICF). The prescreening protocol and related ICF will be made available upon request by the Sponsor.

At screening, subjects will be asked to attend the clinical site to have assessments performed as indicated in the Schedule of Events (Table 2).

¹ V03 from IP dosing schedule and V04 from QIV dose schedule may be combined on same day if V04 occurs at least 28 days after V01. In such case, activities do not need to be duplicated during the visit.

² Prior to dosing. Subjects will be assessed for any known reactions to licensed influenza vaccines.

³ Specifically includes the dermal injection site. A targeted physical examination may be performed on other body systems if indicated based on review of interim medical history or subject symptoms as observed by site or by PI.

All results from the screening procedure needed to evaluate eligibility, including the clinical laboratory results, must be available prior to study vaccination on Day 1. Any abnormal assessment at the screening visit will be assessed according to its clinical relevance, and if found clinically significant, the subject will not be included in the study.

During the screening period, the following procedures and assessments will be carried out for each subject to determine their eligibility for participation in the study:

- Obtain informed consent prior to any procedures being performed
- Record demographics
- Confirm eligibility criteria for enrollment and vaccination
- Obtain medical history
- Record concomitant medications

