- Perform complete physical examination (neurological, rectal and gynecological exams do not need to be performed unless clinically indicated), including height and weight
- Vital signs (blood pressure, heart rate, and body temperature)
- Collect urine for dipstick pregnancy test (applicable females only)
- Collect nasal swab for Covid-19 testing
- Collect blood for serology for HIV, HBV and HCV
- Collect blood for serum chemistry and hematology
- Collect blood for immunogenicity assays
- Urinalysis (dipstick) and urine screen for drugs of abuse
- Record any concomitant therapy/medically attended AEs/SAEs after signing of consent

Beginning at the screening visit and at subsequent visits subjects will be instructed on Covid-19 best practices including wearing a mask in public spaces whether indoors or outdoors, distancing from people outside of their household, frequent washing of hands, etc. At each visit, subjects will be asked a series of scripted questions to evaluate their exposure to Covid-19 and results will be documented in the source.

Unscheduled visits may be planned (up to Day 28) to assess, confirm, and follow-up on out-of-range clinical laboratory test, or vital sign values that determine a subject's eligibility, or in case of a positive urine drug screen. The result of the retest will be considered for subject eligibility. Findings made during unscheduled visits should be reported in the eCRF system.

A record of the number of screening failures and the reasons for screening failure will be captured in a study file. Data for subjects who fail screening or who are not randomized into the study will not be included in the study database. The failure details will be documented in a study file maintained by the site.

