9. ADVERSE EVENT REPORTING

9.1. **Definitions**

Adverse Event

An AE is any untoward medical occurrence in a clinical study subject administered a medicinal (investigational or non-investigational) product. An AE does not necessarily have a causal relationship with the treatment. An AE can therefore be any unfavorable and unintended sign (including an abnormal finding), symptom, or disease temporally associated with the use of a medicinal (investigational or non-investigational) product, and whether related to that medicinal (investigational or non-investigational) product.

This includes any occurrence that is new in onset or aggravated in severity or frequency from the baseline condition, or abnormal result of diagnostic procedures, including clinical laboratory test abnormalities.

AEs will be monitored from the time of consent until Visit 03 (Day 28 after the IP dose administration) and from Visit 04 until Visit 05 (Day 28 after the QIV dose administration). SAEs or medically attended events will be documented from the time of consent until Visit 05.

Serious Adverse Event

An SAE is any untoward medical occurrence that meets any of the following conditions:

- results in death;
- is life-threatening, i.e., the subject was at risk of death at the time of the event (e.g., ventricular fibrillation and anaphylaxis). The term does not refer to an event which hypothetically might have caused death if it were more severe.
- requires inpatient hospitalization or prolongation of existing inpatient hospitalization:
 - Hospitalization refers to an overnight admission into hospital for the purpose of investigating and/or treating the AE. Hospitalization for an elective procedure, or routinely scheduled treatment for a pre-existing condition that has not worsened, is not an SAE.
- results in persistent or significant disability/incapacity, i.e., causing substantial disruption of the subject's ability to conduct normal life;
- is a congenital anomaly/birth defect;
- is medically significant, i.e., may not be immediately life-threatening or result in death or hospitalization but may jeopardize the subject's health or may require intervention to prevent one of the above outcomes. Examples of such events are intensive treatment in an emergency room or at home for allergic bronchospasm, blood dyscrasias, or convulsions that do not result in hospitalization or development of drug dependency or drug abuse.

Unlisted (Unexpected) Adverse Event

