9.2. Adverse Events (AEs)

Adverse events were to be recorded from the day of informed consent through QIV Day 29. For subjects without QIV administration, follow-up for both AEs and SAEs was 28 days after IP. During the study treatment period subjectswere asked non-leading questions to determine the occurrence of spontaneously reported (unsolicited) AEs.

Symptoms were collected for the 7 days following IP administration using eDiaries, with clinical interpretation of data entries by the site investigator. At the discretion of the investigator, a symptom recorded by the subject on the eDiary may have been reported as an AE. The investigator was responsible for determining the severity and the relationship to IP for any eDiary-based AEs. There was no reconciliation of the database between the eDiary symptoms and other AE reports.

PE findings recorded as clinically significant, severe, or life threatening were to be recorded as AEs. Investigators usedtheir judgement regarding reporting of additional PE findings as AEs.

All AEs will be included in the listings. Only treatment emergent AEs will be summarized.

Separate listings of subjects who died, discontinued the study due to an AE, or experienced an SAE will be provided.

Treatment-emergent AEs (TEAE) are AEs with start dates between administration of the IP and IP Day29. If there is no administration of QIV then AE/SAE follow-up will be 28 days post IP administration. However, AEs with start dates past Day 29, if judged by the investigator to be IP-related, will be included in the treatment emergent set.

All AEs will be coded based on MedDRA (V24.0).

Where provided in Protocol Appendix 1, AEs will be graded according to the Vital Sign and Systemic Toxicity Assessments.

N (%) of subjects with at least one TEAE and N (%) of subjects with at least one treatment-related treatment-emergent AE (TRAE) will be summarized. TEAE and TRAE by worst severity will be summarized.

N (%) of subjects with TEAE will be reported by System Organ Class and Preferred Term (SOC/PT) and maximum severity. N (%) of subjects with TRAE will be reported by SOC/PT and maximum severity.

N (%) of subjects with TEAE by SOC/PT by overall frequency (decreasing) will be reported.N (%) of subjects with TRAE will be reported by SOC/PT by overall frequency (decreasing).

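### The primary SAE endpoint runs from consent to 28 days after QIV, but the SAP summarises a different window and plans no SAE count to match it

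*Protocol*

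**What the plan says.** Protocol 2.2.1 gives three primary endpoints. Those for solicited reactions and unsolicited AEs start at administration of M2SR or placebo. The third starts earlier: "The number and percentage of study participants who experience SAEs from the time of informed consent through 28 days after receipt of QIV".

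Collection matches that third window: "SAEs or medically attended events will be documented from the time of consent until Visit 05" (Protocol 9.1). Consent comes before dosing: "Screening for eligible and consenting subjects will be performed within 28 days prior to randomization/IP administration" (Protocol 6.1.2). The same section adds: "Data for subjects who fail screening or who are not randomized into the study will not be included in the study database".

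SAP 9.2 sets the analysis. "All AEs will be included in the listings. Only treatment emergent AEs will be summarized". The window is: "Treatment-emergent AEs (TEAE) are AEs with start dates between administration of the IP and IP Day29". AEs that start later are added if the investigator judges them IP-related. For SAEs the planned output is: "Separate listings of subjects who died, discontinued the study due to an AE, or experienced an SAE will be provided". The protocol's own statistics section (8.3.2) also plans only a listing of SAEs. SAP 9.2 further reports AEs in four start-date windows: following IP, between IP and QIV, within 7 days of IP, and after QIV. SAP section 1 says that it overrides the protocol where they differ.

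**The concern.** The primary objective is the safety of one dose of M2SR. An SAE during screening cannot be an effect of that dose, yet the endpoint wording counts it if the subject goes on to be randomised. The pre-dose part is also incomplete, because SAEs in people who were never randomised are not in the database.

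The SAP does not replace this wording with a usable rule. Its treatment-emergent window is too short for the endpoint, and a listing is not a number and percentage. Whoever programs the report must choose between a count that includes unexposed time and a summary that stops at IP Day 29 for unrelated events. SAP 1.1.2.3 gives the statistician and programming staff treatment codes throughout the trial, which is a further reason to fix the rule in writing before lock. At stake is which SAEs enter a primary safety result, in a trial where a single event is visible in an arm percentage.

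**Working it through.** The documents attach no sample size, power or error rate to this endpoint, so there is no stated figure to reproduce. The check is a comparison of windows, followed by its scale.

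**1. Which SAEs each rule covers, for a dosed subject who receives QIV**

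| SAE onset | Protocol 2.2.1, read literally | SAP 9.2 treatment-emergent summary | SAP 9.2 SAE listing |
|---|---|---|---|
| Consent to IP | counted | not counted | listed |
| IP to IP Day 29 | counted | included among AEs, not shown as SAEs | listed |
| After IP Day 29 to 28 days after QIV, judged IP-related | counted | included among AEs, not shown as SAEs | listed |
| Same period, judged unrelated to IP | counted | not counted | listed |

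The four start-date windows all begin at or after IP, so none admits a pre-dose event. The window after QIV, and the one between IP and QIV, could show AEs that start after IP Day 29. The SAP does not say how these windows fit with summarising only treatment-emergent AEs, and none of them is an SAE count.

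**2. Post-dose time outside the treatment-emergent window**

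IP Day 29 is 28 days after dosing. If QIV is given d days after IP, the post-dose part of the endpoint lasts d + 28 days, of which d + 28 − 28 = d days follow IP Day 29. The share is d/(d + 28).

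- Cohort 3, d = 28: 28/56 = 50%.
- Cohort 3, d = 42: 42/70 = 60%.
- Cohorts 1 and 2: the interval is variable, with first IP expected in June and QIV possibly not available until September (Protocol 1.4). Assuming d = 90: 90/118 = 76%.

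**3. Pre-dose time under the literal protocol wording**

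With s days from consent to IP, the share of the whole window is s/(s + d + 28). With s = 28:

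- d = 28: 28/84 = 33%.
- d = 42: 28/98 = 29%.
- d = 90 (assumed): 28/146 = 19%.

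These are shares of days, not of SAEs. No typical screening length is given. Twenty-eight days is the nominal maximum, although Protocol 6.1.2 provides for screening bloods that are older than that.

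**4. Effect of one event**

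Planned arms are 80 M2SR and 40 placebo (Protocol 3.2). One pre-dose SAE counted literally adds 1/80 = 1.25 points or 1/40 = 2.5 points.

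**5. Illustration of how many such events to expect**

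The documents give no background SAE rate. Assume r between 2% and 15% per person-year, a full 28 days of screening, and nobody excluded because of the event. Then p = 1 − exp(−r × 28/365.25), which is 0.153% to 1.143%.

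- M2SR: 80p = 0.12 to 0.91 events.
- Placebo: 40p = 0.06 to 0.46 events.

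Under the SAP's treatment-emergent rule the contribution to the summarised percentages is 0.

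**The case against.** The strongest reply is that the SAP already settles the matter. It overrides the protocol, summarises only events from IP onward, and lists every SAE. With few SAEs likely in a Phase 1b trial, a reader of the listing can see each one and its timing.

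Much of this stands. A reader might infer from Protocol 2.2.1 that screening-period SAEs will be counted in the M2SR and placebo percentages. The documents do not support that: no table in the SAP would place them there. A reader might also infer that such events would dilute a true difference. They occur before blinded treatment, so in expectation they add equally to both arms and leave the risk difference essentially unchanged; mainly a ratio would move toward 1. SAP 9.2 rules out statistical tests of AE rates. The AE and SAE halting rules in Protocol 7.3 require relatedness to IP, and Protocol 9.3 classes an event without product received as not related. Subjects with a serious event during screening may also fail the eligibility re-check at V01. Nor should the 29% to 33% be read as a share of SAEs: it is calendar time, and it uses the QIV interval that applies only to Cohort 3.

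What does not stand is that the SAP therefore delivers the endpoint. A listing is not a number and percentage. SAP 9.2 does not restate, redefine or drop the SAE endpoint, and SAP section 12, which records changes to planned analyses, does not mention it.

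**Conclusion.** The point holds as a mismatch between a primary endpoint and its analysis, and it is minor. The protocol wording includes unexposed time. The SAP rule excludes that time but also omits, from its treatment-emergent summary, SAEs after IP Day 29 judged unrelated to IP. In Cohort 3 that later period is 50% to 60% of the post-dose window, and more where QIV is given later.

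It would go too far to say that those later SAEs are lost: they are collected to Visit 05, they are in the SAE listing, and they may appear in the start-date windows. What is missing is a specified SAE count by arm over the post-dose window.

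A pre-dose event would matter only if the protocol wording were applied literally: 1.25 points in M2SR or 2.5 points in placebo per event, at the planned arm sizes. Any resulting imbalance would be chance, not systematic bias, and no formal comparison is planned. The expected numbers of pre-dose events rest on assumed SAE rates.

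**What to change.** In Protocol 2.2.1 and SAP 9.2, define the primary SAE endpoint as n (%) of IP Safety Set subjects, by treatment received, with at least one SAE starting at or after IP administration and up to 28 days after QIV. For subjects who receive no QIV, end the window at the follow-up that SAP 9.2 already states, 28 days after IP. Add that table to the SAP, and list SAEs starting before IP separately, outside the count.

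The cost is a short definition in each document, one table and a start-date filter. Collection and expedited reporting of SAEs from consent do not change.
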